IV. Outcome Measures- The primary objective of the pilot study is to evaluate the feasibility of conducting a randomized trial comparing individualized treatment versus usual care for GDM. Our primary feasibility outcomes will be the number (proportion) of women who are eligible, screened, enrolled and remain in the study at each outcome assessment. As pregnant women are a difficult population to retain, we will identify any issues related to recruitment, enrollment and retention that will be necessary to account for when determining the sample size estimated for the future trial. Reasons for exclusion and subject refusal will be tracked at the time of screening by the research team. We will assess reasons for participant attrition through a follow-up call or e-mail at the time of withdrawal. We will determine the proportion of women who remain on the treatment assigned at the beginning of the pilot within each arm. We will review health records to determine the reason for changing treatments. We will measure trough levels at the time of the repeat OGTT. We will also review treatment titration to assess the proportion of participants who are titrated according to the protocol.

V. Analysis Plan – Demographic characteristics, such as race, age, parity, and insurance will be compared between study arms to assess balance and comparability. Descriptive summaries will include the mean and standard deviations (or medians and quartiles for skewed distributions) for continuous variables and frequencies and proportions for categorical variables. Due to the pilot nature of this RCT, hypothesis testing is not the primary focus, but rather estimation within each study arm.

VI. Sample Size - We will introduce the pilot trial to all women undergoing an OGTT. We plan on screening 300 women to allow us to include ~60 women in the pilot study. This sample size

will allow us to have various GDM mechanisms represented. Assuming 30 women within each study arm and a 5% type I error rate, we will have the ability to estimate within-arm 95% confidence interval margin-of-errors of no more than 0.18 for each of our feasibility outcomes.

VII. Study Procedures:

Screening Visit

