Participants will be removed from the study if they eat at unscheduled times during/Preparing for their study visit. This will also interrupt their oral glucose tolerance test. Since subjects will not be able to eat prior to breakfast on the day of the study visit, the research team will be monitoring subjects for signs and symptoms of the hypoglycemia, which include, heart palpitations, sweating, hunger, confusion, abnormal behavior, and visual disturbances. If subjects develop any of these symptoms, standard hospital protocols will be followed. Risks will be evaluated at the study visit through observation of the subject and by eliciting a verbal description of the subject's comfort level.

The principal investigator will terminate the involvement of a given subject in the research study if said subject develops a condition that precludes her from having blood draws or upon meeting any of the exclusion criteria during study participation. This study will be terminated if the risk-to-benefit ratio changes (i.e. risk outweighing benefits is identified during the study).

IX. Compensation:

Participants will receive \$25 for completing the screening procedures, \$75 for completing the repeat 3-hour oral glucose tolerance testing, and \$50 for completing the cord blood and

neonatal body composition assessment. She will be paid a total of \$150 for completing all study procedures.

All payments will be made in the form of a UPMC WePay debit card.

No cash or money orders shall be exchanged between research staff and study participants.

[figure not shown]
No compensation will be provided for partial completion of the research study.

No cash or money orders shall be exchanged between research staff and study participants.

Skinfold Measurements

[figure not shown]
- Take skinfold measurements directly on skin-not through clothing
- Pick up and hold skinfold with thumb and forefinger of one hand (usually left). Apply the jaws of the caliper to the skinfold about $\frac{1}{4}$ to $\frac{1}{2}$ an inch from the fingers holding the fold.
- Measure all skinfold measurements on the **right side**. Do not release the fingers holding the fold. The caliper should only be used to measure the thickness of the fold, not to hold the skin folded. Any pressure placed on the caliper jaws as a result of their holding the skinfold in a folded state will result in an incorrect higher reading.
- **Record skinfold measurements to the nearest tenth of a millimeter (0.1 mm)**

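### Section VIII removes a woman from the whole study for unscheduled eating, even after randomisation, so one invalid repeat OGTT becomes avoidable attrition

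*Combined protocol and SAP*

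**What the plan says.** Section VIII (Participant withdrawal) states: "Participants will be removed from the study if they eat at unscheduled times during/Preparing for their study visit". The next sentence adds: "This will also interrupt their oral glucose tolerance test". The same section has the investigator end the involvement of a woman who "develops a condition that precludes her from having blood draws or upon meeting any of the exclusion criteria during study participation".

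Section VII (Study Procedures) places randomisation at study visit 1. The repeat OGTT, done fasting, is at study visit 3, two weeks after treatment begins. After that come brief research contacts at routine prenatal visits, birth weight and length, cord-blood c-peptide, newborn body composition and record abstraction.

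Section IV (Outcome Measures) states: "Our primary feasibility outcomes will be the number (proportion) of women who are eligible, screened, enrolled and remain in the study at each outcome assessment". Recruitment and retention problems are to be identified so that the investigators can "account for when determining the sample size estimated for the future trial". It also plans: "We will assess reasons for participant attrition through a follow-up call or e-mail at the time of withdrawal".

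**The concern.** The word also in the second sentence of Section VIII makes the interrupted test an additional consequence, separate from removal. On its wording, the rule takes the woman out of the study, not just out of that visit. Visit 3 is a study visit with a stated fasting requirement and falls after randomisation, so the rule reaches randomised women.

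Three things are at stake.

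- **Retention.** A removed woman does not remain in the study in any ordinary sense. A failed fast is then scored as attrition at every later assessment, although she may have been willing to continue.
- **Later data.** The prenatal research contacts and the cord-blood and newborn measurements do not depend on the visit 3 OGTT, but they would end with her participation.
- **Use of the result.** Retention is meant to inform the larger trial's sample size. Section IV does not say how study-imposed removals are counted alongside women who choose to leave.

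**Working it through.** **Sequence in the documents**

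1. Randomisation: Section VII, study visit 1.
2. Fasting repeat OGTT: Section VII, study visit 3, for women who have started treatment. It is the only visit after randomisation with a stated fasting requirement.
3. Removal for unscheduled eating: Section VIII, with no limit to screening or to women not yet randomised.
4. Prenatal research contacts, cord blood and newborn measurements: Section VII, after visit 3 or not tied to it.
5. Continued follow-up of a removed woman, or a repeat of a spoiled test: not mentioned in any section.

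Steps 1 to 3 put randomised women under the rule. Steps 4 and 5 mean that the loss goes beyond the test itself.

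**The plan's own figure**

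Inputs from Section VI (Sample Size): 30 women per arm, 5% type I error, and the ability to "estimate within-arm 95% confidence interval margin-of-errors of no more than 0.18 for each of our feasibility outcomes".

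Wald half-width at p = 0.5: 1.96 × sqrt(0.25/30) = 0.179, which rounds to 0.18. The figure is reproduced and is not in dispute.

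**Cost of one removal**

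- In one arm: 1/30 = 0.033, or 3.3 percentage points.
- Over both arms: 1/60 = 0.017, or 1.7 points.

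These are upper limits. They assume that the woman would otherwise have stayed to the assessment in question. She did attend visit 3, so the cost falls mainly on later assessments.

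Illustration, assuming 27 of 30 would otherwise be retained (Wilson 95% intervals):

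- No removal: 27/30 = 90.0% (74.4% to 96.5%).
- One removal: 26/30 = 86.7% (70.3% to 94.7%).

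**Total effect**

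The documents give no rate of unscheduled eating. If 2%, 5% or 10% of randomised women were removed (an assumption), the expected numbers are:

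- 60 × 0.02 = 1.2 women
- 60 × 0.05 = 3.0 women
- 60 × 0.10 = 6.0 women

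Retention would fall by at most 2, 5 or 10 points. Only women who start drug treatment reach visit 3, so the number exposed there may be below 60.

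**Denominator for a separate OGTT count**

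If 15 to 30 women per arm reach visit 3 (an assumption), one failed fast is 1/15 = 6.7 points to 1/30 = 3.3 points of the proportion with a valid repeat OGTT.

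**The case against.** The other side has several fair points.

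- **The authors may have meant removal from that visit only.** This is possible, but the text says the study and treats the lost test as a further effect. If the narrower meaning was intended, one clarifying line settles it.
- **Attrition reasons are already to be collected.** This stands. Staff would know why they removed a woman, so study-imposed and voluntary losses could be separated from planned data. What it does not do is prevent the loss.
- **A pilot should measure retention under its own rules.** This also stands in part. A total that includes such removals misleads the later sample size only if the larger trial would drop the rule, and the documents do not say whether it would.
- **The delivery and newborn measures are not outcomes in Section IV, and Section V plans no analysis of them.** Correct. Section V is descriptive, with estimation within arms, so no efficacy comparison is at risk.

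A reader might infer more than the documents support. One inference is that all later data are lost. Record abstraction depends on consent and a completed first study visit, with no stated stop on removal, and reasons for treatment changes come from health records. Loss from the treatment-adherence outcome ("We will determine the proportion of women who remain on the treatment assigned at the beginning of the pilot within each arm") is therefore possible but not shown. Another inference is that the effect is large because 3.3 points is a sizeable part of the 0.18 margin. Any single loss in an arm of 30 costs 3.3 points, so that comparison says nothing about how often this rule would operate.

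**Conclusion.** The point holds as an avoidable design weakness of minor to moderate severity. Followed as written, Section VIII turns one invalid test into the loss of a willing randomised woman. It counts against a primary feasibility outcome and ends research measurements that do not need that test.

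The size is up to 3.3 points of retention in an arm per removal. The total is unknown and may be small, since the 2% to 10% range is only an assumption. The conclusion rests on reading Section VIII literally and on the ordinary meaning of remaining in the study.

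A reader might go on to infer that the retention estimate will be materially wrong, that the arms will be affected differently, or that the future sample size will be misdirected. The documents do not support any of these. They give no event rate, no reason to expect a difference by arm, and no statement of the rules the larger trial would use.

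**What to change.** 1. **Section VIII, eating rule.** State that for randomised women a non-fasting visit invalidates that OGTT only and that the woman stays in the study. Set the test to missing, or reschedule it where feasible and record its actual timing.
2. **Sections IV and V, counting.** Keep all randomised women in their arm's denominator. Report own withdrawals and study-initiated removals separately, by arm and assessment. Report valid repeat OGTT obtained as its own count among women who reach visit 3, so that failed fasts stay visible without being scored as attrition.
3. **Section VIII, termination by the investigator.** This is a separate rule. Reconcile it with Sections IV and VII by stating whether, for randomised women, consented record abstraction and delivery and newborn data collection continue after involvement is ended. No clinical or safety decision needs to change.

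**Cost.** Protocol wording and a line in the participant-flow table, with no extra patients. A rescheduled OGTT costs another visit of 3 to 4 hours and moves the test off the two-week point that Aim 2 uses to assess consistency of mechanism. Setting it to missing avoids both costs but loses that woman's repeat OGTT.

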- Fill a pre-prepared red top tube with 4 mL of blood (insulin, c-peptide, free fatty acids)
 1. Gently invert tube five times to avoid clotting
 2. Place sample on ice
 3. Centrifuge sample at 1200 RFG (approximately 3000rpm) at 4°C for 15 minutes

[figure not shown]
Sample processing:

1. Materials and equipment needed per participant

a. During study visit:

- 1.5mL cryovials (**fill each with 1mL**)
- Labels for cryovials which should include subject ID, visit number and sample time following the study's protocol. Please indicate light green (LG) or red (R) on the cryovials to help differentiate samples

Cryovial Label appearance

The blood specimens will be processed at the CTRC and vials will be transferred **WEEKLY** to the central lab for analysis as per Table 2. All remaining vials will be stored at the CTRC at least at -70.

Table 2. Number of microvials to be transferred to the central lab for analysis

Time Intervals (in mins)	Insulin; C-peptide, free fatty acids,	Lipids
Microvial	Red	Green
0	2	1
60	2	
120	2	
180	2	

Women who are diagnosed with gestational diabetes are eligible for the pilot study.

Study visit #1

Each woman will meet with a physician from the study team and be randomized to one of two study treatment groups: individualized therapy or usual care. A randomization sequence will be generated and incorporated into the database prior to recruitment. Permuted block randomization with randomly varying block sizes will be performed by a web-based data entry system.

All women diagnosed with GDM will be started with medical nutritional therapy as per clinical guidelines. The decision to start treatment is based on home glucose values after 1-2 weeks of medical nutritional therapy. Pharmacologic treatment is recommended if fasting values are greater than 95mg/dl or postprandial values are greater than 140mg/dL. Initiation of usual care vs/ individualized treatment will only occur once glucose values exceed these goals despite medical nutritional therapy. Following initiation of pharmacologic therapy, and throughout gestation, home blood glucose levels will be reviewed weekly and the doses of drugs will be adjusted in person during a clinic visit or via telephone per the email.

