Time Intervals (in mins)	Glucose	Insulin; C-peptide, free fatty acids,	Lipids
Microvial	Grey	Red	Green
0	1	2	1
60	1	2	
120	1	2	
180	1	2	

Interviews will occur at the time of the second OGTT for women who are enrolled in the study and at the time of refusal for those who opt out. Interviews will focus on participant/provider perception of study/treatment and whether they experienced any burdens. 16 participants (8 in each group) will be interviewed along with 10 women who decline to enroll in the study but agree to an interview.

Additional study visits:

During a participant's routine prenatal visits (which typically occur every 1-2 weeks) with her provider that occur between 29 and 40 weeks of gestation, she will also meet with a member of the research team who will record information about her blood glucose measurements, pregnancy, weight, and any side effects she had since the last study visit. These study visits will occur in her provider's office and will take no more than 10 minutes to complete.

At the time of labor and delivery

Delivery: At delivery, the hospital research nursing team we will measure infant birth weight and length at delivery. We will collect umbilical cord venous blood for assay of c-peptide. We will only collect these samples if it is safe to do so and possible to do so based on staffing.

Air displacement plethysmography will be used to measure body composition (PEA POD; Life Measurement Inc, Concord, CA) in the newborns within 72 hours post-delivery to provide an estimate of percent body fat and lean body mass.

Data abstraction: Once written consent is provided and participant completes the first study visit, a member of the research team will conduct at least two prenatal and two postnatal EHR data abstraction from the prenatal and delivery records: type of delivery, prenatal and delivery complications. We will also collect information regarding any treatment for gestational diabetes as well as the number of ultrasounds and tests for assessment of fetal well-being (biophysical profiles, non-stress tests).

VIII. Participant withdrawal:

Participants may withdraw from the study at any time.

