The purpose of this research study is to determine the best way to choose medications to treat pregnancy-induced diabetes (called gestational diabetes). In usual care, medications to treat gestational diabetes include insulin, metformin and glyburide. They are used for treatment of diabetes in pregnant and non-pregnant patients. Each of these medications targets a pathway of diabetes and recent studies suggest that women have different pathways for gestational diabetes. We are proposing to match medications to treat gestational diabetes with a woman's unique pathway. You may be eligible to take part in this study because you are being tested for gestational diabetes and may be expected to need medications.

This study includes one screening visit, a study visit and measurements after delivery and to be done here at Magee. The screening visit includes additional blood draws at the time of your 3-hour oral glucose test that was requested by your physician. If you are diagnosed with diabetes then you are eligible to continue in the study. During the course of the study, we will perform research tests and procedures such as drawing blood samples from a vein in your arm, performing brief physical exams, recording your medical history and other research measurements, and asking you to complete a repeat 3-hour oral glucose test 2 weeks after starting treatment. We also will collect blood samples at the time of your labor and delivery of your baby and assess the fat content of your newborn before you leave the hospital.

You will be compensated for your participation in this research study and could receive up to \$150 for completing all portions of the study.

Does this sound like something you would be interested in participating in?
(If No): Thank you very much for calling.

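### The recruitment phone script omits random assignment and the usual-care arm, and its visit sentence conflicts with Section VII

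*Combined protocol and SAP*

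**What the plan says.** **The phone script.** The caller is told "We are proposing to match medications to treat gestational diabetes with a woman's unique pathway". The visits are summarised as follows: "This study includes one screening visit, a study visit and measurements after delivery and to be done here at Magee". The script mentions the extra blood draws at the first glucose test, the repeat test ("asking you to complete a repeat 3-hour oral glucose test 2 weeks after starting treatment"), blood samples at labor and delivery, and the newborn fat measurement. It then asks "Does this sound like something you would be interested in participating in". If the caller says no, she is thanked and the call ends.

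**Section VII of the protocol.** At study visit #1 each woman will "be randomized to one of two study treatment groups: individualized therapy or usual care". Study visit #2 is held at a routine visit and takes at most 10 minutes. Study visit #3 is the repeat glucose test and takes 3-4 hours. Under Additional study visits, at routine prenatal visits between 29 and 40 weeks, "she will also meet with a member of the research team who will record information about her blood glucose measurements"; these contacts also take at most 10 minutes.

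**Section IV.** The primary feasibility outcomes are the numbers and proportions eligible, screened, enrolled and remaining. Reasons for refusal are to be tracked at screening, and the results feed the sample size of the larger trial.

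**The concern.** The pilot exists to learn whether women will accept a randomised comparison of individualised treatment with usual care, and at what burden. The script is silent on randomisation and gives a shorter visit list than the protocol. A woman who declines on the phone cannot have been reacting to randomisation, because she has not been told of it. A woman who says yes has not yet accepted it. If she objects, the objection will surface only at consent or later, unless she raises the matter herself.

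What is at stake is how refusals are read: at which stage they occur and for what reason. The planners of the larger trial will use that record to decide where recruitment loses women. The script adds a second gap, since its If No branches have no place to write a reason although Section IV promises that refusal reasons are tracked.

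**Working it through.** **1. The plan's own figure.** Section VI gives a within-arm 95% margin of error of at most 0.18 with 30 women per arm. At the worst case, p = 0.5:

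1.960 × √(0.5 × 0.5 / 30) = 0.1789, which rounds to 0.18.

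The figure reproduces. It does not depend on the script, and nothing here changes the sample size.

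**2. Script against protocol.**

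- *Allocation.* Script: matching of drugs to pathway only. Usual care appears once, as background to list the existing drugs, not as a group she might join. Protocol: randomisation to two groups at study visit #1, with 30 women per arm assumed, so about half of the 60 would be in an arm the caller was not told about.
- *Numbered study visits.* Script: one, besides screening. Protocol: three. The script's single visit fits visit #3, because the repeat test is described. Visit #1 (the physician meeting and randomisation) and visit #2 are missing.
- *Contacts at prenatal visits.* Script: none. Protocol: brief research contacts at routine visits, which typically occur every 1-2 weeks.
- *Delivery and newborn measurements.* Present in both.

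**3. Where an objection is recorded.** The phone steps are description, interest question, eligibility questions and scheduling. Section VII then places the consent form before the research glucose test, and randomisation after a diagnosis of gestational diabetes. With the current script, consent is the first of these steps at which a phone-recruited woman could decline because of randomisation. With a complete script it would be the phone call. She is not enrolled in either case; only the stage differs.

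**4. What a shift of stage can do to a proportion.** Section IV does not name its denominators. Take enrolled over screened as an example. The planned value is 60/300 = 20%, with a margin of 1.960 × √(0.2 × 0.8 / 300) = 0.045. Suppose, as an assumption only, that 5%, 10% or 20% of the 300 are phone-recruited women who are counted as screened now but would decline on the phone after a full description. The same 60 women enrol:

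- 5%: 60 / (300 − 15) = 21.1%
- 10%: 60 / (300 − 30) = 22.2%
- 20%: 60 / (300 − 60) = 25.0%

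These values show the mechanism and are not estimates. The documents give neither the share recruited by phone nor the share who would object.

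**The case against.** The strongest reply is that the script is only a first contact. Consent is completed before the research glucose test, and a member of the research team explains procedures in person. Phone interest is not a listed outcome. A woman who declines at consent is correctly counted as not enrolled, and screening at the glucose test is where Section IV tracks refusals. The script is worded for women who call in, while Section VI introduces the trial to all women having the test, so few may hear it.

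The gap in burden is also modest. Visit #2 and the prenatal contacts are short and attached to care she already attends. The script's three items correspond to the three paid components in Section IX, and it discloses the most demanding one, the repeat test. Its wording is a proposal to match, not a promise.

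All of this stands, and it limits the consequence. It does not remove the conflict between the script and Section VII, and the points about burden do not touch the omission of randomisation. Good disclosure at consent would itself produce the later recording of refusals described above.

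A reader might go further and infer that enrolment and retention are distorted, with extra losses in the usual-care arm among women who expected a matched drug. The documents do not support that. It would require women to reach randomisation still uninformed. The consent pages were removed from the supplied text, so they cannot be presumed silent.

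**Conclusion.** The discrepancy is certain: the script leaves out random assignment and the usual-care arm, and its visit sentence does not agree with Section VII. The consequence is a possible shift in the stage, and in the recorded reason, of refusals among women recruited by phone. Its size is unknown, and no effect on retention or by arm is shown.

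A total count of omitted contacts would not be sound either. The Abstract allows only 8-10 weeks from diagnosis to delivery, shorter than the 29-40 week window, and visit #2 may coincide with a routine contact. The firm comparison is one study visit stated against three numbered visits plus brief repeated contacts.

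The conclusion assumes that some women are recruited with this script and that no other recruitment wording is read to them before the interest question. The correction is worth making because it is cheap and concerns what the pilot is meant to measure. It does not call the pilot's design or sample size into question.

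**What to change.** 1. Align the visit sentence with Section VII: screening, study visits #1, #2 and #3, short research contacts at routine prenatal visits, and delivery and newborn measurements. Say that visit #2 and the additional contacts take no more than 10 minutes at routine visits, and that visit #3 takes 3-4 hours.
2. Before the interest question, add wording such as: *If you are diagnosed with gestational diabetes and continue in the study, you will be assigned by chance either to treatment matched to your pathway or to usual care. Either approach to medication applies only if you need medication after nutritional therapy.* The second sentence is needed because Section VII starts drug treatment in either arm only when glucose goals are exceeded despite nutritional therapy.
3. Add an optional reason-for-declining field to the If No branches. Without it, the fuller script would move some refusals to a point where no reason is kept. Report refusals by stage (phone, consent, randomisation) and enrolment by recruitment route or script version.

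The cost is a short ethics amendment to recruitment wording and one extra field on the script. Apparent phone interest may fall slightly.
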